#### 1.1 Version History

**Table 1. SAP Version History Summary** 

SAP Version	Associated Protocol Amendment	Approval Date	Change	Rationale
1.0	Protocol amendment 3 dated 07 Apr 2022	05 May 2022	Not Applicable	Original version
2.0	Protocol amendment 3 dated 07 Apr 2022	23 Sep 2022	The description of the Evaluable population in Table 5 was	Correction.

Table 1. SAP Version History Summary

SAP Version	Associated Protocol Amendment	Approval Date	Change	Rationale
			updated to match the	
			description in Table 2.	
			Modifications to text in Table 2, Table 4, and Sections 1.2, 5.1.2, and 5.5.2.	Update or clarification.
3.0	Protocol	25Aug2023	Additions in Table 2,	To perform sensitivity analyses for the
	amendment 3		Table 5, and Sections	primary endpoint according to
	dated 07 Apr 2022		5.1.3, 5.3, and 5.5.	randomised induction groups.
			Additions in	To describe handling of re-screened
			Section 5.1.2.	participants.
			Additions in	To perform KM plots by
			Section 5.4.1.2.	subpopulation.
			Additions in	To define TEAE status when AE onset
			Section 5.4.2.1.	time is missing.
			Additions in	To describe the change from Pre-TM
			Section 5.5.3.	BUP analysis, the timepoints for the change from Pre–RBP-6000 timepoint, and the graphical presentations.
			Additions to Section 5.6.1.	To describe additional summaries and clarify description of some summaries.

**Table 1. SAP Version History Summary** 

SAP Version	Associated Protocol Amendment	Approval Date	Change	Rationale
			Additions in Section 5.6.2.	To clarify analyses descriptions, add 1 category to the TEAE summary, add analysis of Run-in Period.
			Add Sections 5.6.3 through 5.6.7, addition in Section 5.7.1.	To describe analyses of additional parameters that were required for the final analysis.
			Updates in Section 5.7.2.	Update the population for analysis and clarifications.
			Updates in Section 5.7.3 and 5.7.5.	Clarifications of analysis specifications.
			Updates in Section 5.7.6.	Add parameters to be summarised by UDS subpopulation.
			Table 8.	Add abbreviations.
			Update Section 6.2.	Add and clarify changes to planned analyses.
			Update Section 6.4.2, 6.4.4 and 6.4.5	Describe handling of missing data for AEs, prior and concomitant medications,

### 1.2 Objectives and Endpoints

The primary objective of the OLIS is to compare treatment retention of participants following RI or SoC induction onto RBP-6000.

The secondary objective of the sub-study is to evaluate the safety and tolerability of RBP-6000 in participants during the OLIS.

The primary and secondary objectives are presented in Table 2 with their associated estimands.

## **Development of Statistical Analysis Plan Template**

Table 2. Primary and Secondary Estimands

	Estimand Attributes			
Statistical	Variable/			PLS
Category	Endpoint	Population a	IES	(Analysis)
Primary Obj	ective: To compare treatment retention of partici	pants following rapid induction	or SoC induction of	onto RBP-6000 with respect to:
Primary Efficacy Endpoint	Treatment retention at Injection 2, defined as the proportion of participants receiving Injection 2 at the Week 2 Visit among those who received at least 1 dose of TM BUP for induction and did not demonstrate idiosyncratic response to the first dose of TM BUP. Participants who discontinue treatment within the sub-study due to not meeting Inclusion/Exclusion criteria will be excluded.	Evaluable Population for treatment retention/discontinuation	Not applicable: Intercurrent events are not relevant for this endpoint.	Retention rate will be estimated by Bayesian beta-binomial model using non-informative uniform prior, ie, Beta (1,1), within individual induction arms. The posterior distribution of retention rate difference between the 2 arms will be obtained and utilised to calculate the posterior probability of non-inferiority of the RI to SoC induction using a 10% non-inferiority margin or a favourable trend of the RI over the SoC induction. The participants will be analysed corresponding to the induction regimen used ("as treated" b ).
Primary Efficacy Endpoint/ Sensitivity Analysis	As primary	As primary	As primary	As primary. The participants will be analysed corresponding to the induction arm to which they were randomised ("as randomised" ').
Secondary Endpoint 1	Time to treatment discontinuation from the first dose of TM BUP used for induction during the OLIS, defined as the number of days from the first dose of TM BUP from the most recent induction attempt until the last scheduled visit observed during the OLIS.	As primary	Not applicable: Intercurrent events are not relevant for this endpoint.	KM curve presented by the induction arm within the randomisation strata (UDS fentanyl negative vs. positive at the day of first dose of TM BUP) and overall. Participants receiving Injection 3 will be censored administratively at the end of the OLIS; otherwise, participants will be viewed as having discontinued treatment at their last scheduled visit observed during the

Table 2. Primary and Secondary Estimands

	Estimand Attributes				
Statistical	Variable/			PLS	
Category	Endpoint	Population a	IES	(Analysis)	
				OLIS. Retention rate (with 95% CI at specific time point) will be estimated using KM product limit method for each induction arm. Hazard ratio (with 95% CI) of RBP-6000 RI to SoC induction will be estimated using a Cox proportional hazard model, with arm as a single covariate, stratified by the randomisation strata.	
Secondary O	bjective: To evaluate the safety and tolerability of	· · ·	<del>-</del>	·	
Secondary	The proportion of participants reporting	SFAS	While-on-	Descriptive analysis (n, %)	
Endpoint 2	adverse events up to Injection 2.		treatment		
			Missing data		
			will not be		
			imputed		
Secondary	The proportion of participants reporting	SFAS	While-on-	Descriptive analysis (n, %)	
Endpoint 3	adverse events between Injections 2 and 3.		treatment		
			Missing data		
			will not be		
			imputed		

Cl=confidence interval, IES=intercurrent event strategy, KM=Kaplan-Meier, OLIS=Open-label Induction Sub-study, PLS=population level summary, RI=rapid induction, SFAS=sub-study full analysis set, SoC=standard of care, TM=transmucosal, UDS=urine drug screen

- a See Section 4 for details.
- b Actual arm
- c Planned arm

#### **Development of Statistical Analysis Plan Template**

1	

#### 1.3 Study Design

This SAP describes the analysis for the OLIS nested within the main study, which is a randomised, double-blind, parallel group, multicentre study to compare the efficacy, safety, and tolerability of 100mg and 300-mg maintenance doses of RBP-6000 administered every 4 weeks to high-risk, treatment-seeking adult participants with moderate to severe OUD (as assessed by Diagnostic and Statistical Manual of Mental Disorders, 5th Edition [DSM-5]) who use opioids via an injection route and/or use high doses of opioids. The OLIS is designed to compare the treatment retention of all participants inducted onto RBP-6000 using SoC (minimum 7 days of TM BUP per label) with RI onto RBP-6000 treatment.

The OLIS randomisation is implemented using an Interactive Web Response System (IWRS). Participants who meet all of the eligibility criteria and all of the TM BUP dosing criteria are randomised following the first induction day urine drug screen (UDS), at a 2:1 ratio to receive either RI or SoC induction. The induction randomisation number, assigned via the IWRS, used central, blocked, stratified randomisation schedules. The stratification factor is first induction day UDS positive for fentanyl (yes or no). Participants who are randomised but do not receive TM BUP will not be replaced.

The OLIS randomisation schedules were generated using SAS v9.4 using a balanced-across-centres (BAC) approach [Song, 2003]. For the BAC approach, all permuted blocks with specified block size (size=3 with treatment ratio 2:1) were determined. Then the block order was randomly permuted to form a Latin Square, and blocks dynamically allocated to centre at the time of randomisation of the first participant. This approach helps balance the treatment assignments across centres when blocks are left incomplete.

Approximately 489 participants will be enrolled and receive RBP-6000 treatment in the OLIS in order to meet the sample size requirements for the main study.

Two interim analyses (IA) will be performed to allow early declaration of non-inferiority (NI) of RI to SoC induction with respect to treatment retention at Injection 2 (see Section 3 and Section 5.8 for details). If NI is declared at the first IA, then the second IA might not be performed.

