Approval from the sponsor must be obtained for any local laboratory and the laboratory normal ranges utilized to determine eligibility for screening. If a local laboratory is utilized for eligibility, the laboratory samples will also be sent to the central laboratory for the baseline analysis value.

If eligibility is confirmed at the screening visit, participants may complete the induction visit. Participants having same-day screening and induction visits are not required to repeat the UDS, pregnancy test, vitals and ECG for the induction visit.

On induction days, eligible participants will provide a urine sample for a UDS dipstick and pregnancy test (female participants of child-bearing potential only). If a female participant has a positive pregnancy test, she will be discontinued and will not proceed with subsequent assessments. The Investigator will ask him/her to self-report recent drug use (including the use of a TLFB assessment). The Investigator may discuss any positive UDS results with the participant only after completion of the TLFB:

- Participants who report that they have used long-acting opioids within the
 previous 24 hours will not be permitted to proceed with induction until the
 24-hour period has passed. If necessary, induction may be rescheduled. The 1st
 day of the repeat induction should be scheduled within 30 days of informed
 consent.
- 2. Participants who have used short-acting opioids within the previous 6 hours may be permitted to proceed with the induction visit at the discretion of the Investigator.

All concomitant medications used since Screening will be reviewed.

The COWS will then be completed to assess withdrawal symptoms.

Participants must meet **both** of the following criteria to receive TM buprenorphine:

- 1. Have a negative pregnancy test (if female and of childbearing potential)
- 2. Be in withdrawal (COWS score ≥ 8)

If a participant's COWS score is <8, the participant may either be re-scheduled for induction within 30 days of informed consent or remain at the site (at the Investigator's discretion), and the COWS may be repeated until the participant has a score \geq 8. Only when the COWS score is \geq 8 and all pre-TM buprenorphine assessments have been completed may the participant receive TM buprenorphine to begin induction.

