5.2 Inclusion Criteria

A participant must meet **all** of the following criteria to be eligible for inclusion in this study:

- 1. Has signed the informed consent form (ICF) and is able and willing to comply with the requirements and restrictions listed therein.
- 2. Is 18 years of age or older at the time of signing the ICF.
- 3. Currently meets DSM-5 criteria for moderate or severe OUD.
- 4. Has a history of OUD as defined by documented medical history of OUD for at least 90 days immediately prior to providing informed consent.
- Meets at least 1 of these criteria for high-risk opioid use at the Screening visit:
 - a. using opioids via the injection route for an average of 5 or more days per week in the last 4 weeks.
 - b. using at least 500 mg IV heroin equivalent (e.g., 1250 mg IV morphine) or self-reported use of any dose of highly potent synthetic opioids (fentanyl and analogues excluding transdermal patches) for an average of 5 or more days per week in the last 4 weeks by any route (See Appendix 22.8, Morphine Dose Analgesic Equivalence Table).
- 6. Is seeking medication for the treatment of OUD.
- 7. Is an appropriate candidate for opioid partial-agonist MOUD in the opinion of the Investigator or medically qualified sub-Investigator.

- 8. Agrees not to use buprenorphine-containing products other than those administered as part of study treatment for the duration of the treatment period.
- 9. A female participant is eligible to participate if she is not pregnant (as confirmed by a negative serum or urine human chorionic gonadotrophin test, not lactating and, if of childbearing potential, agrees not to become pregnant while on the study and to use medically acceptable means of contraception while on the study). The following methods of contraception are considered to be medically acceptable: established use of oral, injected or implanted hormonal contraception; placement of an intrauterine device or intrauterine system; or use of a double-barrier method of contraception (condom or occlusive cap with use of a spermicide).

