9.4.1 Randomisation into the Open-label Induction Sub-study

The sub-study randomisation will be implemented using an IXRS.

Qualified participants who meet all of the inclusion criteria, none of the exclusion criteria, and all of the TM buprenorphine dosing criteria will be randomised. Eligible participants will be randomised following the first induction day UDS, at a 2:1 ratio to receive either rapid induction or SoC induction. The induction randomisation number will

be assigned via the IXRS, using central, blocked, stratified randomisation schedules. The randomisation factor is first induction day UDS positive for fentanyl (yes or no).

Participants who are randomised but do not receive TM buprenorphine will not be replaced.

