9.5 Blinding

Participants, Investigators and site personnel not involved in performing injections of RBP-6000 will be blinded to study medication during the DBTP (Injections 3 to 10). The blinding of the study will be maintained through several mechanisms.

- An IXRS system will be used, which will track the randomisation for each study participant and will also assign the treatment that the participant will receive. The IXRS will be responsible for subsequent assignment of all RBP-6000 doses.
- Each study site will have an unblinded study drug manager and an unblinded drug administrator who will have no other responsibilities in the clinical trial. These roles can be fulfilled by the same or multiple individuals. The person who administers the treatment must be a healthcare provider, who is familiar with giving injections.
- At each injection visit in the DBTP (Injections 3 to 10), a unblinded staff member will contact IXRS to obtain the treatment assignment.
- The unblinded staff member will then obtain and prepare the RBP-6000 for administration. Because of volume and size differences between RBP-6000 containing 100 mg or 300 mg buprenorphine, study participants and site personnel must be shielded from seeing the syringe prior to and during the injection. The unblinded staff member will apply a large blank label around the barrel of the syringe several times, to mask the volume and size of the injection. RBP-6000 preparation will occur in a separate room away from blinded study staff and the participant.

Once RBP-6000 has been prepared, the unblinded study drug administrator will
administer RBP-6000 to the participant as described in the applicable product
labelling information. RBP-6000 administered will be tracked via IXRS and drug
accountability logs will be maintained for each participant, which the unblinded study
drug manager will complete.

The Open-label Induction Sub-study will be open label.

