22.2 Schedule of Events – Rapid Induction Day 1 (Injection 1)

Visit Name (Window)	Firs	t Induction Day ¹ / I	Repeat Induc	tion Day		Week 1 Da	y 1		
Timepoint	Check in ²	Pre-TM BUP	TM BUP	Post- TM BUP	Pre-RBP-6000	RBP-6000	Pos	t RBP-6	5000
Planned Time			-1 hr			0 hr	1 hr	2 hr	4 hr
Urine Pregnancy Test ³	X								
UDS ⁴	X								
Self-Reports/TLFB ⁵	X								
COWS ⁶	X			X ⁷			X	X	X
AE Assessment and Concomitant Medications ⁸	-								—
Dosing Criteria	X ⁹			X ¹⁰					
Open-Label Randomisation ¹¹	X								
Vital Signs ¹³		X			X ¹⁴				
12-Lead ECG ¹⁵		X							
TM Buprenorphine Administration ¹⁶			X						
300-mg RBP-6000 Administration						X			
Injection Site Evaluation ¹⁹							X	X	
Counselling ²⁰	-								→

AE=adverse event; COWS=Clinical Opiate Withdrawal Scale; ECG=electrocardiogram;

TLFB=TimeLine Follow Back; TM=transmucosal; UDS=urine drug screen

Confidential Page 126 of 147

- 1. See Figure 3 for rapid induction Day 1 induction flow chart.
- 2. Procedures are the same for all participants before randomisation (see flow chart in Figure 2).
- Required for female participants of child-bearing potential only. Participants with positive pregnancy tests (urine test confirmed by serum test) will be
 discontinued. Participants having same-day screening and induction visits are not required to repeat the test for the induction visit.
- 4. Qualitative on-site dipstick to be performed. Investigator to discuss any positive UDS results with participant after the completion of the TLFB. Participants having same-day screening and induction visits are not required to repeat the test for the induction visit.
- 5. Details participant's daily drug use for each of the past 7 days, in addition to capturing the main route of use (and more specifically, if an injectable route was used), and number of times used per day.
- 6. Per Investigator discretion, participants with COWS <8 may either remain at the site and repeat assessments later that same day or be re-scheduled to return on another date. The COWS performed at 1 and 2 hours post-dose are to be performed ±15 minutes. Additional COWS may be repeated at any time, per Investigator discretion. Participants having same-day screening and induction visits are required to complete all the required COWS assessments for each visit, per the schedule of events (i.e., screening, induction check-in, post TM-BUP, and post RBP-6000).

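### Fixed blocks of 3 by centre in the open-label 2:1 induction sub-study let a site that infers the block length foresee up to 4/9 of its allocations, and no planned analysis examines this

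*SAP*

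**What the plan says.** SAP 1.3 describes a balanced-across-centres scheme. For its one block size, "all permuted blocks with specified block size (size=3 with treatment ratio 2:1) were determined"; the block order is then permuted into a Latin square, with "blocks dynamically allocated to centre at the time of randomisation of the first participant". The schedules are also stratified: "The stratification factor is first induction day UDS positive for fentanyl (yes or no").

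Protocol 9.5 says of masking: "The Open-label Induction Sub-study will be open label". A site therefore sees every allocation it has received. It also knows the stratum before it randomises, because Protocol 22.2 specifies for the drug screen: "Qualitative on-site dipstick to be performed", and its note 11 requires the fentanyl result before randomisation.

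The protocol itself gives no block length. Section 9.4.1 says only that numbers are assigned "using central, blocked, stratified randomisation schedules".

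Some judgement comes before allocation. Inclusion criterion 7 reads "Is an appropriate candidate for opioid partial-agonist MOUD in the opinion of the Investigator or medically qualified sub-Investigator". Under Protocol 4.1.1, a participant with a COWS score below 8 "may either be re-scheduled for induction within 30 days of informed consent or remain at the site".

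The primary analysis (SAP 5.3.2) is a beta-binomial comparison by induction arm received, without centre or stratum. Its one sensitivity analysis (SAP 5.3.3) regroups participants by randomised arm.

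**The concern.** With two rapid (R) slots and one SoC (S) slot per block, only RRS, RSR and SRR exist. Once S has appeared, every remaining slot in that block is R; after RR, the next is S. In an open-label trial, a site that has worked out the length can read off these slots. If it enrols or defers participants with the next arm in mind, the arms stop being comparable at the moment of randomisation.

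The claim at stake is non-inferiority of rapid induction on retention at Injection 2. The tabulated overall type I error is already 9.2% to 9.8% against a limit of 10% (SAP Table 3), so even a small bias towards rapid induction exceeds the limit. Regrouping by randomised arm does not help, because the selection would happen before randomisation.

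**Working it through.** **Inputs.** Block size 3 at 2:1, by centre and fentanyl stratum (SAP 1.3). N = 489, that is 326 rapid and 163 SoC, with looks at 120 and 240 (SAP 3). Beta(1,1) priors, and success if the posterior P(rapid − SoC > −10 points) is at least 96% (SAP 5.3.2). The null case is 70% SoC and 60% rapid (SAP Table 3).

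**1. Reproducing the plan.** The rule was simulated with looks at 80/40, 160/80 and 326/163. Power at 70% in both arms is 77.4%, against 77.2% stated. Overall type I error at 70%/60% is 9.4%, against 9.41% stated.

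**2. Share of allocations known in advance.** The three blocks are equally likely. Position 1 is never certain, position 2 is certain with probability 1/3 (after S), and position 3 is always certain.

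- Complete block: (0 + 1/3 + 1)/3 = 4/9 = 44.4%.
- Rapid slots: on average 1 of the 2 per block is certain, or 50%.
- SoC slots: the single slot is certain with probability 1/3, or 33%.
- The best guess is right 77.8% of the time, against 66.7% from always guessing rapid.

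For n participants in one centre and stratum, the expected share is [(complete blocks × 4/3) + (1/3 if two are left over)]/n:

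| n | 1 | 2 | 3 | 4 | 5 | 6 | 20 |
|---|---|---|---|---|---|---|---|
| Known | 0% | 16.7% | 44.4% | 33.3% | 33.3% | 44.4% | 41.7% |

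For example, n = 5 gives (4/3 + 1/3)/5 = 33.3%. The realised share cannot be computed, because the number of sites is not given.

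**3. What steering could do.** The documents give no figure for the effect of steering. Assume it changes expected retention in known slots by d points, with d from 2 to 5. If all known slots are used in both arms in favour of rapid induction, the bias is d × (1/2 + 1/3) = 0.83d: 1.7 points at d = 2 and 4.2 at d = 5. If half are used, it is half of that. If only known rapid slots are raised, it is 0.5d. Putting the shifted rates through the simulation in step 1, with complete blocks:

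| Assumed behaviour | Type I error, d = 2 | Type I error, d = 5 |
|---|---|---|
| None | 9.4% | 9.4% |
| Half the known slots, both arms | 12.1% | 17.3% |
| Known rapid slots only | 12.7% | 19.6% |
| All known slots, both arms | 15.4% | 29.6% |
| All known slots, against rapid | 5.5% | 2.3% |

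**4. What other block lengths give.** A fixed block of 6 leaves 13/45 = 28.9% certain. A random, undisclosed mix of 3 and 6 leaves about 9% (18 allocations per centre and stratum, with the observer knowing the candidate lengths). The best guess is then still right about 75% of the time, so partial predictability remains.

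**The case against.** **Site knowledge is not shown.** The length appears only in the sub-study SAP, and nothing shows that sites received it. This stands as a condition on the finding. But neither document says the length was withheld, and a site can infer it from its own open-label sequence.

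**44% is a ceiling.** A reader might infer that 44% of the trial's allocations were predictable. The documents do not support that. A site must follow each fentanyl stratum separately, and SAP 1.3 itself expects incomplete blocks. A reader might also infer from the Latin square that still more was predictable. The SAP does not say that a centre receives each permutation once per set, so that reading has no support either.

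**Discretion is limited.** Deferral under Protocol 4.1.1 is tied to a COWS score below 8 or to recent opioid use. A participant who meets the dosing criteria is to be randomised (4.1.2). Eligibility waivers are barred (5.8). Rescreening needs Medical Monitor approval and is closed once a participant has been randomised (5.9). These limits narrow the route but do not close it: criterion 7 and the decision to proceed after recent short-acting opioid use are judgements made before allocation.

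**The type I error figures rest on assumptions.** Size, direction and uptake of steering are all assumed, and steering against rapid induction would make the test conservative. This stands, and is why a range is shown.

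**The list may be past changing.** SAP 1.3 says the schedules were already generated, and version 3.0, dated 25 August 2023, adds analyses for the final analysis. Few unused blocks may remain. This shifts the weight to the analysis.

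**Conclusion.** The concern holds as a weakness of the design. A single short block length, used by centre in an open-label 2:1 comparison, makes up to 4/9 of allocations knowable in advance to a site that has the length, and fewer where blocks are incomplete. Under assumed shifts of 2 to 5 points towards rapid induction, type I error goes from about 9.4% to between 12% and just under 30%, depending on how many known slots are used. Every such case exceeds the stated 10%; steering the other way gives about 5% to 2%.

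A reader might infer that selection took place or that a non-inferiority result would be invalid. Nothing in the documents shows either. What they show is an opportunity and the lack of any planned analysis that would reveal whether it was used.

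**What to change.** **Randomisation.** For blocks not yet allocated, use randomly varied lengths in multiples of 3, for example 3 and 6. Hold the lengths in the restricted randomisation file rather than in the SAP. State whether the length was withheld from sites.

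**Analysis, in all cases.** Add one sensitivity analysis of the primary endpoint that keeps all participants and stratifies by, or adjusts for, the conditional probability of rapid allocation given earlier allocations in the same block. With blocks of 3 this is 2/3 at the first position, 1/2 after R, 1 after S or after one of each, and 0 after RR. Test whether retention within each arm depends on it. The levels 0 and 1 each contain one arm only, so they inform the arm comparison through a model term; pure stratification would rest on the levels 1/2 and 2/3. The SAP should say which is used.

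**Excluding determined participants** should be descriptive only. With complete blocks it leaves 326 × 1/2 = 163 rapid and 163 × 2/3 ≈ 109 SoC. Single-look power at 70% retention in both arms falls from about 73% to about 52%, and the remaining set mixes 2:1 and 1:1 positions.

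**Cost.** One extra analysis from data already held. If the list is changed, there is slightly more imbalance within small centres and some loss of the balanced-across-centres property, which is built on a single block size.
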